## Abstract

**Please Note, [name] transferred from the Pittsburgh VA to the Ann Arbor VA, HSR&D Center for Clinical Management Research (CCMR) in August 2023. All research activities for AIM 1, AIM 2 and the recruitment, enrollment, and intervention activities of AIM 3 were completed at the Pittsburgh VA before her station transfer to the Ann Arbor VA. We are requesting regulatory approval for the remaining research activities for AIM 3 only. These activities are limited to completing the extraction, cleaning, and analysis of AIM 3 outcome data from the VA's electronic health record (via the Corporate Data Warehouse). Additionally, the study team may pull data from CAPRI/Joint Legacy Viewer (JLV) to examine notes, charts, dates of AUDIT-C administration and other details to validate the accuracy of our AIM 3 dataset.**

Objectives: Unhealthy alcohol use is common among Veterans and a significant risk factor for numerous negative health consequences, including chronic disease, injury, mortality, and suicide. It is also linked to increased financial and societal costs (e.g., higher healthcare utilization, criminal justice expenses). Due to these burdens, effective, evidence-based care for Veterans with unhealthy alcohol use was implemented in VA primary care (PC) settings. However, significant gaps in this care have been identified, indicating that a substantial proportion of Veterans in need of help are not receiving it. This study used an evidence-based implementation strategy called practice facilitation, at the VA Pittsburgh, to pilot test whether practice facilitation has the potential to improve the quality of PC-based alcohol-related care.

Research Plan: We are requesting IRB approval for the remaining research activities for AIM 3 only. These activities are limited to completing the extraction, cleaning, and analysis of AIM 3 outcome data from the VA's electronic health record (via the Corporate Data Warehouse). All research activities for AIM 1, AIM 2 and the recruitment, enrollment, and intervention activities of AIM 3 were completed at the Pittsburgh VA.

Methods: **Aim 1**(completed at the Pittsburgh VA) utilized qualitative methods to assess Veteran and PC stakeholders to understand barriers and facilitators to high-quality alcohol care, which was then used to help refine and hone the practice facilitation intervention. **Aim 2** (completed at the Pittsburgh VA) included focus groups with a sample of PC providers to assess the acceptability and feasibility of the refined practice facilitation intervention. **Aim 3** pilot tested the finalized practice facilitation intervention in the full PC clinic (this pilot implementation intervention was completed at the Pittsburgh VA) to understand whether practice facilitation improves the quality of PC-based alcohol-related care. The AIM 3 outcome data analysis will take place at the Ann Arbor VA utilizing the VA electronic health record (via the Corporate Data Warehouse).

---

(Please double click the correct box below):

☒ This Study **WILL** use the VA electronic health record (EHR) or EHR Data on or after Jan. 2019 (for example: entering notes; entering consults; ordering labs, medications, procedures, imaging, etc.; eligibility screening with EHR chart review or CDW; using CDW data; etc.).

☐ This Study will **NOT** use the VA electronic health record (EHR) or EHR Data on or after March 2022 (for example: entering notes; entering consults; ordering labs, medications, procedures, imaging, etc.; eligibility screening with EHR chart review or CDW; using CDW data; etc.).

## **List of Abbreviations**

Provide a list of all abbreviations used in the protocol and their associated meanings.

AUD: Alcohol use disorder

AUDIT-C: Alcohol use disorders identification test- Consumption survey

BI: Brief intervention

CCMR: VA Center for Clinical Management Research

CDW: VA Corporate Data Warehouse

DART: VA Informatics and Computing Infrastructure Data Access Request Tracker

DoD: Department of Defense

HIPAA: Health Insurance Portability and Accountability Act

HSR&D: VA Health Services Research and Development Service

IRB: Institutional Review Board

PACT: Patient Aligned Care Teams

PC: VA primary care

PHI/PII: Protected Health Information/Personally Identifiable Information

PTSD: Post-traumatic stress disorder

OI&T: VA Office of Information and Technology

SSN: Social Security Number

VA: Veterans Affairs

VHA: Veterans Health Administration

VINCI: VA Informatics and Computing Infrastructure

**2.0 Introduction**

Unhealthy alcohol use is common among Veterans and a significant risk factor for numerous negative health consequences, including chronic disease, injury, mortality, and suicide. It is also linked to increased financial and societal costs (e.g., higher healthcare utilization, criminal justice expenses). Due to these burdens, effective, evidence-based care for Veterans with unhealthy alcohol use was implemented in VA

primary care (PC) settings. However, significant gaps in this care have been identified, indicating that a substantial proportion of Veterans in need of help are not receiving it.

### 3.0 Objectives

Previous work on this study conducted at the Pittsburgh VA included utilizing qualitative interviews with Veteran and PC stakeholders to understand barriers and facilitators to high-quality alcohol care and to help refine and hone a practice facilitation intervention (**AIM 1**), conducting focus groups with a sample of PC providers to examine the acceptability and feasibility of the practice facilitation intervention (**AIM 2**), and conducting a pilot test of the finalized intervention in the full PC clinic (**AIM 3**). Research activities at the Ann Arbor VA that [name] will be conducting are limited to completing the extraction, cleaning, and analysis of AIM 3 outcome data from the VA's electronic health record (via the Corporate Data Warehouse). Additionally, the study team may pull data from CAPRI/Joint Legacy Viewer (JLV) to examine notes, charts, dates of AUDIT-C administration and other details to validate the accuracy of our AIM 3 dataset.

## **5.0 Study Procedures**

### **5.1 Study Design**

**AIM 1:** *Ann Arbor regulatory approval is not requested for this AIM. All study activities were completed at the Pittsburgh VA.* Aim 1 was conducted to further understand barriers and facilitators to high-quality alcohol care, and to use the findings to develop and hone the practice facilitation intervention. Recruited from a single primary care clinic at the Pittsburgh VA, remote-based, semi-structured and open-ended, 1-on-1, interviews with key clinical stakeholders and Veteran patients with unhealthy alcohol use were conducted. Clinical stakeholder interviews focused on clinicians' prior experiences working with Veterans with unhealthy alcohol use, elicit perceptions and attitudes towards alcohol-related care, and elicit feedback on using practice facilitation to improve alcohol-related care. Interviews with Veterans asked about preferences and needs related to alcohol use and to explore how primary care can best support Veterans in achieving goals related to cutting back or abstaining from drinking. Feedback on the practice facilitation helped to ensure that providers, staff, and Veterans were receptive to the practice facilitation content.

**AIM 2:** *Ann Arbor regulatory approval is not requested for this AIM. All study activities were completed at the Pittsburgh VA.* Aim 2 delivered the refined practice facilitation to a group of primary care providers and staff, recruited to assess its feasibility and

acceptability. Based on participant feedback, the practice facilitation was revised again in preparation for the pilot implementation intervention in Aim 3. The facilitator conducted the focus groups with recruited PC staff and providers as a way to practice delivering the material, refining the material, and to assess whether material was acceptable and feasible in the primary care setting.

**AIM 3:** *Ann Arbor regulatory approval is being requested for only the data analysis portion of AIM 3 (extraction, cleaning, and analysis of AIM 3 outcome data from the VA's electronic health record (via the Corporate Data Warehouse)). All AIM 3 recruitment, enrollment, intervention, and survey activities were completed at the Pittsburgh VA.* AIM 3 recruited providers and staff in the primary care clinic at the Pittsburgh VA. The facilitator met with primary care staff/providers as a group to introduce the final version of the practice facilitation. During the early months of the intervention, the facilitator, observed clinicians as they cared for patients with unhealthy alcohol use. It was essential for better understanding clinic workflow and where gaps in knowledge occur. While the facilitator observed clinic workflow, she excused herself when providers or patients requested it. She observed providers use of the electronic health record and typical workflow as providers triaged and treated patients with unhealthy alcohol use. Additionally, the facilitator conducted ongoing monthly meetings with a small subset of primary care participants interested in championing this care and communicated regularly via email with the clinic champions for ongoing support. Ongoing meetings discussed ways to improve alcohol-related care, based on "Plan Do Study Act" or "PDSA" cycles, to help providers identify gaps in alcohol care and test solutions to optimize care quality. Educational handouts for providers and patients were developed and distributed and training sessions regarding evidence-based alcohol care (e.g., medications for alcohol use disorder, motivational interviewing overview to improve brief interventions) was offered when providers expressed a desire for more training and education on this topic. Any trainings that occurred were based on VA/DoD clinical guidelines for treating substance use disorders, thus part of routine clinical activity.

### **Evaluation of the Practice Facilitation Intervention: Implementation and Clinical Outcomes.**

Aim 3 implementation and clinical-specific outcomes were derived guided by the RE-AIM (Reach, Effectiveness, Adoption, Implementation, and Maintenance) evaluative framework, often used to guide implementation evaluations. RE-AIM will be assessed using EHR data pulled from VA's Corporate Data Warehouse (CDW). The data pull will include data from January 1, 2019 – December 31, 2023, to evaluate these outcomes, which includes the pre-intervention period, the active facilitation intervention period, and the post-facilitation intervention period (i.e., 3-, 6-, and 12-months after active implementation). RE-AIM constructs are defined as follows:

**Reach** of alcohol-related care will be assessed at the patient level using EHR data, pulled from VA's CDW. **Reach** outcomes will be expressed as a rate, with the

denominator (for all outcomes) defined as all Veterans with a visit to the Pittsburgh VA primary care clinic during the practice facilitation intervention. The numerator for each Reach outcome is as follows: the number of Veterans who screened positive for unhealthy alcohol use (AUDIT-C  $\geq$  5) AND had any documented brief intervention, encounters with primary care-mental health integration (PC-MHI), encounters with PACT/ Whole Health clinical pharmacists, specialty addictions treatment (inpatient and outpatient clinic visits for substance use disorder treatment encounters with an accompanying AUD diagnosis), or pharmacotherapy for AUD (any filled prescription for FDA-approved medications: acamprosate, disulfiram, or oral/injectable naltrexone or non-FDA approved effective medications: gabapentin, baclofen, or topiramate) in the 30 days following a positive screen. Denominators will also be derived to represent specific subpopulations (e.g., women, Black and Hispanic Veterans). Rates at the start of the practice facilitation intervention and at 3- and 6-months post intervention will be calculated to examine change in Reach outcomes over time.

**Adoption** is identified as the percentage of providers from the PC clinic who deliver alcohol-related care when a Veteran screens positive for unhealthy alcohol use. Specifically, we will use data available in the EHR to examine delivery of brief interventions, consults placed to PC-MHI/clinical pharmacists or specialty addictions treatment and providing pharmacotherapy for AUDs at the provider and clinic level. Rates of alcohol-related care pre-intervention (2019-2022), during the course of the practice facilitation intervention (July 2022-December 2022), after the intervention (e.g., 3- and 6-months post intervention (Jan 1, 2023-March 31, 2023, and Jan 1, 2023-June 30, 2023 respectively) will be used to measure whether adoption rates of alcohol-related care increased over time.

**Maintenance** is defined as the extent to which evidence-based alcohol care becomes routine and part of the PC culture (care sustained over time). Reach and Adoption outcomes using EHR data will be assessed at 12-months post intervention (Jan 1, 2023-Dec. 31, 2023) to examine whether high-quality alcohol care was sustained.

**Effectiveness** is defined as the prevalence of unhealthy alcohol use at 12-months post-intervention (Jan 1, 2023-Dec. 31, 2023) as measured by AUDIT-C scores pulled from the EHR. This variable will also be expressed as a rate with the denominator defined as all Veterans with a visit to PC during the practice facilitation intervention (same as for Reach outcomes). The numerator will be the number of Veterans with an encounter in PC who screened positive for unhealthy alcohol use (AUDIT-C  $\geq$  5) at 12-months post facilitation intervention. While it is unlikely that a pilot study will have a measurable

impact on clinical outcomes, measuring effectiveness will serve as pilot data for a larger trial.

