#### **5.7 Data Analysis**

**Implementation Outcomes:** Reach outcomes will be reported descriptively (e.g., percentage of patients with an AUDIT-C  $\geq 5$  who were offered a BI or pharmacotherapy for AUD) and compared pre- (2019-2022) and post-implementation (at 3- and 6-months) to see whether Reach of alcohol care increased over time. Adoption outcomes via EHR will be descriptive, and include percentages, frequencies, and means (SD) of alcohol-related care by provider and clinic to understand whether Adoption of high-quality alcohol-related care increased over time. Descriptives will be examined and compared at the start of Active Implementation and at 3- and 6-months post Active Implementation. Reach and Adoption rates will again be examined at 12-months post Active Implementation and compared to rates at 3- and 6-months to see if high-quality alcohol-related care was sustained (Maintenance). **Effectiveness outcomes:** Effectiveness will be assessed via a time-series analysis, where the intervention site will serve as its own control, and we will investigate whether Veterans' with an encounter in Pittsburgh VA Primary Care during the implementation intervention reduced their drinking 12-months post intervention using AUDIT-C scores in the EHR. Time-series analysis was chosen because historical trend is accounted for in the analytic model, results can be displayed graphically, and the size of the effect can be estimated at different times post

intervention. The outcome (AUDIT-C scores) will be modeled using a regression model with an indicator for practice facilitation (pre- vs. post-), a continuous term for time (days since practice facilitation dissemination) and the interaction between the two. The indicator variable will assess immediate changes in AUDIT-C scores post implementation intervention, while the interaction term will assess if there is a change in the slope of AUDIT-C scores pre- and intervention at 12-months. While there is controversy over whether pilot studies should assess clinical efficacy or effectiveness, we decided to examine it here as a training opportunity and as preparation for a possible hybrid effectiveness-implementation Merit trial investigating practice facilitation as a way to improve alcohol-related care on a larger scale.

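### Sections 5.1 and 5.7 give Reach different denominators; under the Section 5.1 version, change in care is confounded with prevalence, screening and window length

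*Combined protocol and SAP*

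**What the plan says.** **Section 5.1, evaluation subsection.** Reach has a "denominator (for all outcomes) defined as all Veterans with a visit to the Pittsburgh VA primary care clinic during the practice facilitation intervention". The Adoption paragraph dates that intervention July to December 2022. The numerator is "the number of Veterans who screened positive for unhealthy alcohol use" (AUDIT-C of 5 or more) and who also had at least one of the listed services, documented or filled, "in the 30 days following a positive screen". The Effectiveness paragraph reuses this denominator and says that it is the one used for Reach. Section 5.4 limits inclusion to the same group, and Section 5.2 puts the data pull at about 10,000 Veterans.

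**Section 5.7.** Reach is described, by way of example, as the "percentage of patients with an AUDIT-C" of at least 5 "who were offered a BI or pharmacotherapy for AUD".

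**Timing.** Section 5.1 says: "Rates at the start of the practice facilitation intervention and at 3- and 6-months post intervention will be calculated". Section 5.7 says that Reach will be "compared pre- (2019-2022) and post-implementation (at 3- and 6-months) to see whether Reach of alcohol care increased over time". Dates for the 3- and 6-month windows (January to March and January to June 2023) appear only under Adoption. The 12-month window for Reach (January to December 2023) is dated under Maintenance. Section 5.7 then compares the 12-month rates with the 3- and 6-month rates to judge whether care was sustained.

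**The concern.** The two sections describe different quantities. One is the share of all clinic visitors who were both positive and given care. The other is the share of positive screens followed by care. The numerators differ as well: a service documented or filled in Section 5.1, a service offered in Section 5.7.

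Facilitation is meant to improve what happens after a positive screen. A rate over all visitors also depends on how many are screened and how many are positive, and over a fixed cohort it depends on how long the window is. The plan draws directional conclusions from Reach (whether it increased, whether it was sustained), and those conclusions could differ by section. The outcome analysis is still to be done, so an unsettled definition could be chosen after the results are seen.

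**Working it through.** The plan states no Reach rate, prevalence, screening rate or target, so there is no figure to reproduce. Every rate below is an assumption; only N = 10,000 and the dates come from the documents.

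**1. Identity.** Let s be the share of the fixed cohort screened in a window, p the share of those who are positive, and c the share of positives who receive care within 30 days.

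- Section 5.1: Reach = (N × s × p × c) / N = s × p × c. It cannot exceed s × p.
- Positive-screen denominator, as in Section 5.7: Reach = c.

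With s = 1 and c = 60%, the Section 5.1 version gives 3% at p = 5%, 6% at p = 10% and 12% at p = 20%. The other version gives 60% each time.

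**2. Prevalence (s = 1).**

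| Scenario | Section 5.1, before to after | Positive-screen, before to after |
|---|---|---|
| c stays 60%, p falls 10% to 8% | 6.0% to 4.8% | 60% to 60% |
| c rises 60% to 75%, p falls 10% to 8% | 6.0% to 6.0% | 60% to 75% |
| c rises 60% to 75%, p stays 10% | 6.0% to 7.5% | 60% to 75% |

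In the third row 7.5/6.0 = 75/60 = 1.25, so the all-visit rate follows care when nothing else moves. At 12 months Effectiveness has the same denominator and window, so Reach is Effectiveness × c: if unhealthy drinking falls, Reach falls with care unchanged.

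**3. Nested windows.** A Veteran counted in January to March 2023 is also counted in January to June and in January to December. With a fixed N, Reach at 3 months ≤ Reach at 6 months ≤ Reach at 12 months. This needs no assumed rate, only that the dated windows and the fixed cohort apply to Reach.

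For illustration, take even once-a-year screening (s = 3/12, 6/12, 12/12), p = 10% and c = 60%:

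- Care constant: 0.25 × 0.10 × 0.60 = 1.5%, then 3.0%, then 6.0%. At 70% annual coverage: 1.05%, 2.1%, 4.2%.
- No care after any screen from July 2023 on: the numerators are 150, 300 and 300, so Section 5.1 gives 1.5%, 3.0% and 3.0%. Care has stopped, yet 12-month Reach equals the 6-month rate and is twice the 3-month rate. With positive-screen denominators of 250, 500 and 1,000, the rates are 60%, 60% and 30%.

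**4. Long baseline against a short window.** If the Section 5.7 baseline runs January 2019 to June 2022, it is 42 months long. With p and c constant, the ratio of post to pre Reach is the ratio of the s values.

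- Even yearly screening, capped at 1: 0.25/1 = 0.25, a 75% fall at 3 months; 0.50/1 = 0.50, a 50% fall at 6 months.
- Random screening at one per year, s = 1 − exp(−months/12): 0.221/0.970 = 0.23, a 77% fall at 3 months; 0.393/0.970 = 0.41, a 59% fall at 6 months.

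Repeat screens in the long window would widen the gap. Cohort members who were not yet clinic patients in 2019-2022 would narrow it.

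**The case against.** Several points on the other side have force.

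- An all-visit denominator is a legitimate population measure. Conditioning on a positive screen has its own weakness: if facilitation changes who is screened or detected, the denominator moves with the intervention. This stands, and it is a reason to report both rates.
- A reader might infer that Reach under Section 5.1 cannot show improvement at all. The third row of the table shows otherwise: with stable prevalence, stable screening and equal windows it tracks care. What it cannot do is separate care from those other factors.
- A reader might take Reach to be the study's main test. The documents name no primary outcome. Adoption also looks at care after a positive screen, though with providers as the denominator.
- The phrase about all outcomes in the Section 5.1 definition refers to types of outcome, not to periods. That one fixed cohort serves every period is an inference, though Section 5.4 supports it. The 3- and 6-month dates are stated only under Adoption, and Section 5.1 takes its Reach baseline at the start of the intervention, not over 2019-2022. The window findings are therefore conditional.
- Section 5.7 offers its percentage only as an example, so the all-visit wording might be thought to govern. But the plan does not say so, and the example is not a case of the Section 5.1 definition. Nor is the all-visit wording a slip, since Effectiveness repeats it.
- Reach is descriptive, in a single-clinic pilot, with no test attached. That limits the consequences, but the plan still reads the direction of change from these rates.

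**Conclusion.** The point holds as an unresolved conflict between Sections 5.1 and 5.7 and, if Section 5.1 is followed, as confounding of change in care with prevalence, screening and window length. The conflict and the identity follow from the text alone.

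Two consequences are conditional. If the windows dated under Adoption and Maintenance apply to Reach with the fixed denominator, Reach cannot fall from 3 to 6 to 12 months, and the Maintenance comparison cannot detect a loss of care. If the multi-year baseline of Section 5.7 is also used, the comparison with a 3-month window is biased against facilitation.

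The size of the bias cannot be derived from the documents. The falls of 75% to 77% at 3 months and the 1.5%, 3.0%, 6.0% sequence are illustrations under assumed rates, and a reader should not take them as estimates for this clinic.

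**What to change.** Use one definition in Sections 5.1 and 5.7, and name the periods to which it applies, including the baseline.

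- **Denominator, per period:** Veterans in the study cohort with an AUDIT-C of 5 or more recorded in that period; the first positive screen in the period is the index.
- **Numerator:** those among them with the documented or filled service within 30 days of the index. Say *received*, not *offered*, in both sections.
- **Alongside, per period:** percent screened and percent positive, with the all-visit rate kept as a secondary population measure.

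**Cost.** Within the existing cohort this is a wording change made before the analysis dataset is built; Section 5.2 already lists AUDIT-C, brief intervention, pharmacy and service-use data. The downsides are these:

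- The denominator is smaller: 500 to 2,000 instead of 10,000 at p = 5% to 20% with s = 1. That need not weaken the comparison of care. For 60% against 70% at p = 5%, illustrative power (two-sided 0.05, independent groups) is 91% with 500 positives per period, against 51% with 10,000 visitors.
- Facilitation may change who is screened or detected. The added percentages help expose this but do not remove it.
- Nested windows still dilute a late loss of care (60% to 30% in the example above, although care had stopped). Showing July to December 2023 separately would make it plain.
- Under Section 5.4, positives before and after the intervention are only those also seen in July to December 2022. Either state this as a limitation, or widen inclusion to all clinic visitors in each period, which would change Section 5.4 and the data pull.

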## **5.2 Recruitment Methods**

Ann Arbor regulatory approval is being requested only for the data analysis portion of AIM 3 (extraction, cleaning, and analysis of AIM 3 outcome data from the VA's electronic health record via the Corporate Data Warehouse). All recruitment, enrollment and intervention activities were completed at the Pittsburgh VA.

Approximately 10,000 Veterans' data will be pulled from the CDW to examine implementation and clinical outcomes. Data to evaluate implementation and clinical effectiveness outcomes will be obtained electronically and securely from already collected administrative databases, using scrambled SSN or Patient ICN to link data together. Data sources will include the CDW, Health Factors (AUDIT-C and Brief Intervention information), Vital Status File to obtain DOB for calculating age of Veterans, and Prescription/Pharmacy information (for data on whether medications for alcohol use disorder were prescribed). Other specific records include: sociodemographics (e.g., sex, gender identity, marital status, indicator of socioeconomic status, race/ethnicity, sexual orientation), past-year diagnoses (Alcohol use disorder diagnosis, Substance use disorder diagnoses, Tobacco use disorder diagnosis, Mental Health disorder diagnosis (Depression, anxiety, PTSD, Bipolar, Psychotic-spectrum)), index of medical complexity (e.g., Charlson index, VA CAN score) utilization of primary care services pre-implementation (2019-2022), during (July 2022 - Dec. 2022) and post-implementation intervention (Jan 2023 - Dec. 2023), referral and utilization of substance use services in the past year (yes/no), and referral and utilization of past-year mental health services (yes/no). Data may also be reviewed within CAPRI/Joint Legacy Viewer (JLV) to allow study team members to look into potential data anomalies from our dataset. In addition, members of the study team may review notes, charts, dates of AUDIT-C administration, etc. to verify the accuracy of our Aim 3 dataset.

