#### **5.4 Inclusion/Exclusion Criteria**

We will include all Veterans with a visit to the Pittsburgh VA primary care during the practice facilitation intervention.

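### The specialty-treatment and pharmacotherapy parts of Reach do not separate new from continuing alcohol care, which dilutes the pre/post change and can bias it if the already-treated share shifts

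*Combined protocol and SAP*

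**What the plan says.** The Reach definition is in section 5.1, under Evaluation of the Practice Facilitation Intervention. A Veteran enters the numerator with an AUDIT-C of 5 or more and at least one of five kinds of care: brief intervention, a PC-MHI encounter, a clinical pharmacist encounter, specialty addiction treatment, or AUD pharmacotherapy. The timing condition is "in the 30 days following a positive screen".

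- The two components at issue are "specialty addictions treatment (inpatient and outpatient clinic visits for substance use disorder treatment encounters with an accompanying AUD diagnosis), or pharmacotherapy for AUD".
- The drug component takes "any filled prescription for FDA-approved medications: acamprosate, disulfiram, or oral/injectable naltrexone", plus gabapentin, baclofen and topiramate.
- The denominator is "defined as all Veterans with a visit to the Pittsburgh VA primary care clinic during the practice facilitation intervention", and section 5.4 adds no exclusion: "We will include all Veterans with a visit to the Pittsburgh VA primary care during the practice facilitation intervention".

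None of these passages looks at what happened before the screen. Section 5.2 does list "referral and utilization of substance use services in the past year (yes/no" among the variables to be pulled, but neither 5.1 nor 5.7 uses it to define or stratify Reach. Section 5.7 reports Reach descriptively, compares 2019-2022 with 3 and 6 months after the intervention, and looks at it again at 12 months for Maintenance.

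**The concern.** Section 2.0 describes the gap that the study addresses as "indicating that a substantial proportion of Veterans in need of help are not receiving it". A Veteran who already attends an addiction clinic, or already refills an AUD medication, is not in that gap. If that Veteran screens positive, the next scheduled visit or refill within 30 days still scores as reached. This holds even where the care is plainly for alcohol, so the AUD-diagnosis condition on specialty visits does not remove it.

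What is at stake is how the change in these two components is read. Part of each rate reflects how many positive screeners were already in treatment, not what primary care did after the screen. The results are meant to inform a possible larger trial, so a diluted or biased change could mislead its planning.

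**Working it through.** The plan gives no expected rate, effect size or power for Reach, so there is no figure to reproduce. Section 5.7 plans no test of Reach, so I quote none.

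**Model (positive screens; specialty visits and drug fills only).** Let s be the share already in treatment, c the proportion of those with a visit or fill within 30 days, and r the rate of new care in the rest. All three are assumptions.

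Measured rate: R = c·s + (1 − s)·r

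**Stable share.** With s and c the same in both periods, the continuing-care term cancels:

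change in R = (1 − s)·(r_post − r_pre)

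Take c = 0.9 and new care rising from 5% to 10% (5.0 points, ratio 2.00):

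| s | R pre | R post | Change (points) | Ratio |
|---|---|---|---|---|
| 10% | 0.090 + 0.045 = 13.5% | 0.090 + 0.090 = 18.0% | 4.5 | 1.33 |
| 15% | 0.135 + 0.0425 = 17.75% | 0.135 + 0.085 = 22.0% | 4.25 | 1.24 |
| 25% | 0.225 + 0.0375 = 26.25% | 0.225 + 0.075 = 30.0% | 3.75 | 1.14 |

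The absolute change loses exactly the fraction s. The ratio loses more, because continuing care raises the baseline.

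**Range.** With c = 1 and the same 5% to 10% rise:

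- s = 5%: 9.75% to 14.5% (4.75 points, ratio 1.49).
- s = 40%: 43% to 46% (3.0 points, ratio 1.07).

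Where new care is already common, the loss matters less. With new care rising from 30% to 40% and s = 10%, R goes from 37% to 46%: 9.0 of 10 points, ratio 1.24 against 1.33.

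**Shifting share (c = 1).**

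- False rise: new care flat at 10%, s from 10% to 15%. R goes from 0.10 + 0.90 × 0.10 = 19.0% to 0.15 + 0.85 × 0.10 = 23.5%.
- Masked rise: new care from 10% to 15%, s from 15% to 10%. R is 0.15 + 0.85 × 0.10 = 23.5% before and 0.10 + 0.90 × 0.15 = 23.5% after.

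**Maintenance (c = 0.9).** Suppose new care in 2023 is at its baseline 5%, but s has gone from 10% to 15%. R goes from 13.5% to 0.135 + 0.0425 = 17.75%, an apparent gain with no sustained change in new care. One way this could happen: a Veteran starts treatment in July-December 2022, is still in it in 2023, screens positive again, and counts through continuing care.

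**Denominator.** Section 5.1 divides by all Veterans with a visit, not by positive screens. That multiplies every R above by the proportion screening positive. If that proportion is stable, the ratios are unchanged and the absolute changes scale down together.

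**The case against.** The strongest reply is that Reach is judged by change over time and continuing care enters both periods. That stands. A reader might infer that continuing care is credited to facilitation, or that it hides any change in new care. The documents support neither. With a stable share, the measured rate still rises in every scenario above. Credit or full masking needs the share to shift, and the documents give no evidence that it does, or in which direction.

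The point is also confined to part of Reach. The figures cover two of five kinds of care. Brief intervention is much less exposed. Section 5.1 speaks of a numerator for each Reach outcome, and the example in 5.7 names brief intervention and pharmacotherapy, so components may be reported separately. If Reach is instead one composite, the base rate and the dilution differ from those shown.

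Preferring new care is also partly a choice of estimand. The study aims to improve the quality of alcohol-related care in primary care, and the proportion of positive screeners in care is a legitimate coverage measure. Nor do the documents show that facilitation cannot affect continuing treatment: the training offered included AUD medications. Adoption counts consults placed, which is closer to new referral, but its pharmacotherapy part has no new-start rule either.

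These replies argue for keeping the current rate. They do not supply a way to tell new care from continuing care.

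**Conclusion.** The point holds for the specialty-treatment and pharmacotherapy components. As written, they count care already under way at the screen. With a stable already-treated share, this dilutes the absolute pre/post change by that share and the ratio by more. With a share that differs between 2019-2022 and 2023, it can bias the change either way, and Maintenance inherits the problem.

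The size cannot be derived from the documents. Every rate in the working is an assumption. A reader might conclude from the table that most specialty and drug events are continuing care, but that follows only from the inputs. At s = 10%, continuing care is 9.0 of 13.5 points before and 9.0 of 18.0 (half) after. For a descriptive pilot outcome, this is a gap in definition that should be closed before the Reach code is written; it does not invalidate the measure.

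**What to change.** In sections 5.1 and 5.7, keep the current Reach rate as overall coverage. For specialty treatment and for pharmacotherapy, each taken separately, also report a new-care rate before and after the intervention:

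- **Denominator:** positive screens with no care of that same type in the prior 90 days.
- **Numerator:** those with a first such encounter or fill in the next 30 days.
- **What counts as care of that type:** specialty encounters with an AUD diagnosis; fills of acamprosate, disulfiram or naltrexone; fills of gabapentin, baclofen or topiramate only with an accompanying AUD diagnosis. The last condition keeps Veterans who fill those three drugs for other reasons in the denominator. The same condition should apply in the numerator, so that their routine refills do not score as new care.
- **Start date:** screens on or after April 1, 2019. The pull begins January 1, 2019, and 31 + 28 + 31 = 90 days gives a complete look-back.

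The cost is some SAP wording and one filter on encounters and fills that the pull already needs. The new-care denominator is smaller. Three of the 42 months from January 2019 to the start of facilitation in July 2022 are lost for this rate. Some Veterans whom primary care re-engages, with a last visit or fill within 90 days, will be classed as continuing; the overall coverage rate still counts them.
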